## **11 PARTICIPANT RIGHTS AND CONFIDENTIALITY**

### **11.1 Institutional Review Board (IRB) Review**

This protocol and the informed consent documents and any subsequent modifications will be reviewed and approved by the IRB and the Scientific Review Committee responsible for oversight of research at the University of North Carolina at Chapel Hill. The IRB application, modification and renewal procedures will be adhered to throughout the study.

### **11.2 Informed Consent Forms**

Interested caregivers meeting the screening criteria for eligibility in the study will be given a copy of the informed consent form (ICF) in the presence of the research assistant. The research assistant will read the ICF to the potential participant pointing out important aspects in each section and answering any questions. The caregiver may choose to sign the ICF at that time or to make another appointment for the research assistant to return. The ICF will describe the purpose of the study, the procedures to be followed, reasons not to be in the study, the risks and benefits of participation, responsibilities of the participant, incentives and remunerations, privacy and confidentiality measures, and the names and contact information for the PI and the study staff. After the caregiver agrees to participate and signs the ICF, the research assistant will sign. If verbal consent, the staff member will indicate verbal consent was given on the consent form. A copy will be given to each caregiver and this fact will be documented in the participant's record.

Because care partners may live at some distance from the caregiver, a telephone consenting procedure will be implemented. The procedure will include all of the aspects of the written consent, but will enable interested care partners to give their verbal consent over the telephone. Each care partner will receive a copy of the ICF in the mail. Their verbal consent will be documented in their record.

### **11.3 Participant Confidentiality**

Participant confidentiality will be maintained according to the Health Insurance Portability and Accountability Act (HIPAA). Research records arising from this study will be retained at a secure UNC-maintained locked site for 15 years with access limited to the PI and named designees.

Any data, forms, reports, and other records that leave the site will be identified only by a participant identification number (Study ID) to maintain confidentiality. All paper records will be kept in a locked file cabinet. All computer entry and networking programs will be done using Study IDs only. Information will not be released without written permission of the participant, except as necessary for monitoring by IRB, the FDA, the NIA, and the OHRP.

### **11.4 Study Discontinuation**

The study may be discontinued at any time by the IRB, the NIA, the OHRP, the FDA, or other government agencies as part of their duties to ensure that research participants are protected.

## **12 ETHICAL CONSIDERATIONS**

The guiding ethical principles being followed by this study are in accordance with international policy, e.g. the Declaration of Helsinki, regarding ethical principles for medical research involving human subjects, and include the following considerations:

- that the study is designed to act in the best interests of our participants' health and well-being, and in fact participation in the study, which involves training in a mind-body intervention, is likely to improve their well-being;
- that it is designed to safeguard their health, including not over-burdening them with questionnaires and making sure that the intervention – which is a telephone based mindfulness training intervention, is reasonable in terms of amount of time being spent, and is evaluated in terms of safety, effectiveness, accessibility and quality;
- that it promotes equity and protection of the subjects' health and rights; that it recognizes that individual research subjects' rights and interest take precedence over the generation of new knowledge; that it protects the dignity, health, privacy and confidentiality of personal information of the research subjects by carefully following IRB procedures;
- that it causes minimum harm to the environment by minimizing amount of paper used where possible;
- that the research team members are all qualified and well trained health professionals competent to perform this research, and that they have taken the Good Clinical Practice training;
- that participants are appropriately compensated monetarily, but without being coerced into being in the study, and that they are expected to benefit from their participation in this research, with little or no harm expected to be caused by their participation in this research;
- that the confidentiality of data is carefully protected, and the consent forms appropriately describe any risks that could be caused, due to any breach of confidentiality, as well as possible benefits;
- that the research is being carried out on a non-vulnerable population, who are capable of giving informed consent;
- that the research was assessed via peer review and found to follow generally accepted scientific principles, and be based on a thorough knowledge of the scientific literature;
- that the design and proposed performance of the study is clearly described and justified in a research protocol, which has been submitted for review;
- that the protocol contains a statement (as described here) of the ethical considerations involved and addressed in this study;
- that the study is being submitted for consideration, guidance and approval to the UNC Committee on the Protection of Human Subjects, and that the principal investigators and the research team will provide monitoring information to the committee, especially any information about serious adverse events;
- and that the researchers plan to submit a final report of their study's findings and conclusions.

## **13 COMMITTEES**

The study includes a Safety Monitoring Committee and an Advisory Council. The Safety Monitoring Committee will review adverse event data over the course of the study. The

Advisory Council will review study procedures and the intervention manual and make recommendations for study improvements.

## **14 PUBLICATION OF RESEARCH FINDINGS**

Publication of the results of this trial will be governed by the policies and procedures of the University of North Carolina. Any presentation, abstract, or manuscript will be made available for review by NIA prior to submission.

## Supplementary Materials

### 15.1.1 Appendix A.1: Periodic Telephone Administered Adverse Event Monitoring Form

STUDY ID: \_\_\_\_\_

Date: \_\_\_\_\_

**1. In the past week**, have you:

a. been hospitalized for any reason?  No  Yes (Please explain):

b. experienced any life-threatening events?

c. given birth to a child with birth defects?

d. become physically disabled in some way?

e. experienced any new or worsening emotional health problems (for example, worry, nervousness, sadness, or stress)?  No  Yes (Please explain, including if participant feels change is related to study participation):

Also, if yes, administer the PROMIS Anxiety SF. *If the participant's T scores increase by >9 points and the T score is >65, consult with the PIs.*

e. experienced any new or worsening physical health problems that you think might be related to being part of this study?  No  Yes (Please explain):

---

*Signature of study personnel completing form*

Master Protocol  
Caregiver Grant (R21 AG061728-01)

---

*Print Name*

Page 46 of 55

---

*Date*

version 5.0  
April 12, 2023

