## 7 **SAFETY ASSESSMENTS**

The risks leading to adverse experiences for participants enrolled in the study are minimal, but do exist. Potential adverse experiences for participants as a result of the telephone-delivered mindfulness intervention include:

- Emotional or psychological discomfort or distress, including:
  - Avoidance
  - Agitation
  - Anxiety
  - Difficulty focusing
  - Irritability
  - Nervousness
  - Obsessive thoughts
  - Panic
  - Restlessness
- Physical symptoms associated with emotional/psychological discomfort or distress:
  - Body or joint aches (resulting from intervention practices)
  - Headaches (resulting from intervention practices)
  - Heavy sweating (without performing strenuous activity)
  - Hyperventilation or rapid breathing (without performing strenuous activity)
  - Nausea or gastrointestinal problems (outside of sickness)
  - Rapid heart rate (without performing strenuous activity)

Study staff will encourage participants that they do not have to answer any questions that make

them feel uncomfortable on study questionnaires. During intervention sessions, participants will be encouraged to participate, but can choose not to do an activity that makes them feel uncomfortable. Study staff and the intervention instructor will make participants aware of the experiences that can occur prior and during their time in the study. Study staff will encourage participants to report emotional distress/discomfort and physical symptoms during intervention sessions and through follow-up calls with study staff, which will occur up to 3 times during the intervention. Adverse events will be captured using the Periodic Telephone Administered Adverse Event Monitoring Form.

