## **7.3 Adverse Events and Serious Adverse Events**

The study team, led by the PIs, will monitor all participants for 3 categories of events: adverse events (AEs), serious adverse events (SAEs) and unanticipated problems (UPs). These three categories are defined as follows:

Adverse event (AE): Any unfavorable and unintended change in physical or mental health status (i.e. new or worsening physical or mental health signs, symptoms, or disease) associated with participation in the study, regardless of whether it is considered related to the study.

Serious Adverse Event (SAE): Any AE that:

- Results in death
- Is life threatening, or places the participant at immediate risk of death from the event as it occurred
- Requires or prolongs hospitalization
- Causes persistent or significant disability or incapacity
- Results in congenital anomalies or birth defects

Unanticipated problems (UPs) involving risks to subjects or others to include, in general, any incident, experience, or outcome that meets all of the following criteria:

- Unexpected in terms of nature, severity, or frequency given (a) the research procedures that are described in the protocol-related documents, such as the IRB-approved research protocol and informed consent document; and (b) the characteristics of the subject population being studied;
- Related or possibly related to participation in the research (“possibly related” means there is a reasonable possibility that the incident, experience, or outcome may have been caused by the procedures involved in the research); and
- Suggests that the research places subjects or others at a greater risk of harm (including physical, psychological, economic, or social harm) than was previously known or recognized.

This study uses the following AE grading scale:

- Mild: An experience that is transient and requires no special treatment or intervention. The experience does not generally interfere with usual daily activities. In this study, an example includes mild emotional distress that persists after a class session has ended.
- Moderate: An experience that is alleviated with simple therapeutic treatments. The experience impacts usual daily activities. In this study, an example includes moderate emotional distress requiring counseling.

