## **8 INTERVENTION DISCONTINUATION**

### **8.1 Discontinuation of Intervention for a Participant**

Participants will be discontinued if adverse events cause:

- Cognitive impairment that prevents participant's understanding or ability to comply with study requirements; or
- Emotional distress that results in psychosis or hospitalization for psychological trauma.

In these situations, study staff will continue to follow-up until participants are under the care of their provider.

Participants may voluntarily withdraw their participation in the study at any time and for any reason. We anticipate that the family care team may wish to withdraw at the time of the death of the care recipient. Participants will continue to be followed, with their permission, even if withdrawal occurs prior to all study activities being completed. All participants that withdraw early, but continue to be followed, will receive follow-up calls to complete the *Telephone Administered Adverse Event Monitoring Form*. Participants will be asked to complete the *Final Evaluation* for the study (see [Section 6.1.4](#)) at the same time point of those in their cohort. If participants withdraws prior to completing all study activities and refuses to be followed, they will be instructed to connect with their primary care provider for any unresolved adverse events and asked to complete the *Final Evaluation* for the study (see [Section 6.1.4](#)) at the time of withdrawing from the study.

If the withdrawal rate is higher than anticipated (see [Section 9.3](#)), additional cohorts may be recruited to reach an adequate sample size.

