## 9.3 Interim analyses and Stopping Rules

We do not plan an interim analysis. The study will be stopped if 3 or more individuals have a serious adverse event probably or definitely related to the study.

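### The telephone adverse event form asks only about physical disability, which is narrower than the SAE criterion in section 7.3: cognitive incapacity is never asked about and mental incapacity is reached only indirectly

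*Combined protocol and SAP*

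**What the plan says.** Section 7.3 defines an adverse event as "Any unfavorable and unintended change in physical or mental health status", so both domains are covered. One of its five criteria for a serious adverse event (SAE) is that the event "Causes persistent or significant disability or incapacity". Nothing limits this to physical disability. Item 8 of the AE Reporting Form (Appendix A.2) has a disability/incapacity box that is also unrestricted.

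Section 7 names the collection instrument: "Adverse events will be captured using the Periodic Telephone Administered Adverse Event Monitoring Form". That form (Appendix A.1) has six questions about the past week, lettered a to d and then e twice:

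- Item d asks whether the participant has "become physically disabled in some way".
- The first item e asks whether the participant has "experienced any new or worsening emotional health problems (for example, worry, nervousness, sadness, or stress". A yes leads to a free-text explanation, including the participant's view on relatedness, and to the PROMIS Anxiety short form. The escalation instruction is: "If the participant's T scores increase by >9 points and the T score is >65, consult with the PIs".
- The second item e covers physical problems only, and only those the participant thinks may be due to the study.

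Section 8.1 lists two adverse event consequences that lead to discontinuation. One is cognitive impairment that prevents understanding or compliance. The other is "Emotional distress that results in psychosis or hospitalization for psychological trauma". Section 9.3 uses the SAE count: "The study will be stopped if 3 or more individuals have a serious adverse event probably or definitely related to the study".

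**The concern.** The form is the routine route by which events reach the study team, and one of its SAE prompts is narrower in domain than the criterion it stands for. The omitted part is the one closest to this intervention's foreseen harms. Section 7 lists emotional and psychological reactions first and describes the physical symptoms as accompanying them. Section 2.2 notes that the training can worsen dissociation in susceptible people. Section 8.1 names cognitive impairment, and it gives psychosis as an alternative to hospitalization, so the plan itself contemplates serious mental events without an admission.

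SAE status matters because it drives 24-hour reporting (sections 7.2 and 7.4; section 7.6 for deaths and related or possibly related SAEs) and the stopping rule in section 9.3. A prompt that leaves out part of the definition weakens the first step of that chain.

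**Working it through.** No arithmetic decides this point, and the plan gives no figure to reproduce. The check sets the form beside the definition it serves.

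| SAE criterion in 7.3 | Prompt on the monitoring form | Match |
|---|---|---|
| Death | None possible from the participant | Not applicable |
| Life-threatening | Item b | Yes |
| Hospitalization, new or prolonged | Item a, for any reason | Yes |
| Disability or incapacity | Item d, physical only | Partial |
| Congenital anomaly or birth defect | Item c | Yes |

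Items a to d therefore cover the four criteria that a participant can be asked about, and only item d departs in domain. Its degree is looser than 7.3, because it carries no persistence or significance qualifier.

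The next step is to see where a non-physical incapacity without hospitalization would be elicited.

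1. *Cognitive incapacity.* Items a to d: no. First item e: it asks about emotional health, and its examples are worry, nervousness, sadness and stress. Second item e: physical only. No item names thinking or memory.
2. *Mental incapacity.* Items a to c: not unless the event is also life-threatening. Item d: no. First item e: yes, as a new or worsening emotional problem with free text, but with no question about loss of function. The form's own escalation depends on an anxiety score rising by more than 9 points and exceeding 65. An anxiety score does not measure cognitive impairment, dissociation or psychosis.
3. *After a report.* Sections 7.1 and 7.5 send any event that is not plainly mild to the principal investigator and the Study Physician. By 7.3 a mild event generally leaves daily activities undisturbed, so an incapacitating event, once reported, should go to that review. The 7.3 text for the Severe grade, however, mentions only hospitalization as the thing that turns the event into an SAE. It gives no cue to the disability criterion.

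On size: 32 dyads give 32 × 2 = 64 participants, and the stopping threshold of 3 individuals is 3/64 = 4.7% of them. If three qualifying events occurred and one went unrecognised, the count would be 2 and the rule would not be met. That holds for any threshold of three. Without an event rate or a sensitivity for the form, neither of which the documents give, it does not yield an expected number of missed events.

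**The case against.** The strongest reply is that the monitoring form is a symptom prompt and that seriousness is decided elsewhere. The AE Reporting Form carries the unrestricted category. Sections 7.1 and 7.5 require review of anything beyond plainly mild. Section 7.6 sends events that are more than mild and possibly related to the principal investigators at once, and 7.5 adds weekly check-ins until resolution. There are other routes of detection too: item a catches psychiatric admission, instructors prompt follow-up of emotional or physical difficulties (7.2), staff ask people who withdraw about adverse events (6.1.4), and those who withdraw early but agree to follow-up keep receiving the calls (8.1). Section 2.2 says adverse events are rarely reported in mindfulness studies.

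Most of this stands. A reader might infer from item d that mental incapacity is not asked about at all, that it would be filed as an ordinary adverse event, and that it would miss the 24-hour report and the stopping count. The documents do not support that chain. The first item e takes any new or worsening emotional problem, with free text and no relatedness condition, and the review rules apply whichever item elicited the event. The anxiety-score trigger adds to those rules and does not replace them.

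What the reply leaves open is narrower. The safeguards act only once a participant volunteers the problem or someone notices it. None of them asks the 7.3 disability question outside the physical domain, and none prompts for cognitive change.

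**Conclusion.** The mismatch is real and small. Item d is narrower than the 7.3 criterion and than the reporting form it feeds. Cognitive incapacity, which 8.1 foresees, is asked about in no item. Mental incapacity without hospitalization is reached only indirectly, through the emotional health item and the review of events that are not plainly mild.

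This is a low-severity safety-ascertainment gap. Feasibility, acceptability, the sample size and the planned analyses are untouched. The conclusion assumes that calls follow the printed form, that participants answer the questions as worded, and that the review in 7.1 and 7.5 works as written. A missed 24-hour report or an untriggered stopping rule remains a possibility of unknown size and should not be stated as a consequence.

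**What to change.** Reconcile item d with section 7.3 by keeping that section's qualifiers and removing the physical restriction. For example: *developed any lasting or significant disability or inability to function, whether physical, emotional/mental, or in thinking or memory?* Have any yes checked against the existing 7.3 definition under the existing SAE reporting rules. No new timeline is needed, and the SAE definition, the 8.1 rules and the stopping threshold stay as they are.

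The qualifiers matter. A question about being unable to do usual activities, without them, would drift toward the Severe grade in 7.3, which is distinct from an SAE, and with a one-week recall it would pick up passing illness.

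The cost is an IRB form modification and some extra yes answers to classify. If the monitoring calls are already complete, the equivalent step is to re-read the free text under the first item e and the recorded reasons for withdrawal against the 7.3 disability criterion.

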## **7.2 Methods and Timing for Assessing, Recording, and Analyzing Safety Parameters**

Timing for assessing, recording, and analyzing safety and adverse events will be completed in the following ways:

- **Assessing:** instructors will prompt the study staff to follow-up with any participants that is endorsing emotional or physical difficulties during the telephone sessions to further assess for adverse experiences.  
  
Study staff will contact participants up to 3 times during the intervention to complete the Periodic Telephone Administered Adverse Event Monitoring Form to assess for safety and adverse events (see Supplementary Materials).
- **Recording:** study staff will document safety and adverse events in the Adverse Event Reporting Form (See Supplementary Materials).
- **Analyzing:** all safety and adverse events will be reviewed by the PI, or a designee to assess the severity and level of follow-up needed for each participant. Moderate and severe level AEs will also be reviewed by the Study Physician, as needed. All reported events will be reported to the Safety Monitoring Committee and IRB for review twice a year and annually, respectively. SAEs will be reported to the Safety Monitoring Committee and IRB within 24 hours of the study staff receiving the report from a participant.

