## 7.6 Safety Monitoring

Study staff will collect data on AEs and UPs on an ongoing basis from study start to study completion.

General AE Procedures. The project manager or study staff will report all AEs to the PIs monthly using the Adverse Event Reporting Form, after having gathered all necessary details. Study staff will report AEs that are more than mild and possibly related to study participation to the PIs right away. Together the PIs will determine the severity and the relatedness of the AE, and will confer with the SMC and the Study Physician, [name], as needed. If the AE is serious and/or unexpected, possibly related to study participation, and suggests increased risk for participants, the procedures outlined below will also be followed.

AE reports will be collected by the project manager or study staff, summarized and de-identified. A summary report of all AEs to date will be sent to the PIs at each monthly full-team meeting.

All AEs will be summarized as part of the Data and Safety Monitoring Report submitted subsequent to the second, fourth, sixth, and eighth 8-week sessions to the SMC and NIA program officer. As per UNC IRB guidelines, all AEs will be reported to the UNC IRB during the yearly study review process.

Serious AE Procedures. The project manager or study staff will report all SAEs to the PI immediately using the Adverse Event Reporting Form, after having gathered all necessary details. For all deaths and for any SAE related or possibly related to study participation, the PI will send this report and any additional information, including corrective actions already taken, within 24 hours to the SMC chair, UNC IRB and NIA program officer. The PI will follow any additional course of action recommended by the UNC IRB, NIA, and/or SMC. All other SAEs (not unanticipated or related) will be summarized and reported to the SMC and the NIA Program Officer quarterly.

Unexpected and Related AEs/UPs with increased risk. All AEs that are deemed 1) unexpected; 2) possibly or probably related to study participation; and 3) suggests increased risk for study participants will be reported to the UNC IRB, NIA project officer, and the SMC chair within 48 hours of study team awareness of the event, using each organizations' respective reporting formats. In these reports, the PI will identify any corrective action planned or already undertaken. The PI will follow any additional course of action recommended by the UNC IRB, NIA, and/or SMC.

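### The adverse event call form looks back one week at 2 to 3 calls and asks about general physical problems only if the participant suspects the study, which does not match Sections 7.3 and 7.6

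*Combined protocol and SAP*

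**What the plan says.** Section 7.3 defines an AE as an unfavorable change in physical or mental health "associated with participation in the study, regardless of whether it is considered related to the study". Section 7.6 sets the collection period: "Study staff will collect data on AEs and UPs on an ongoing basis from study start to study completion".

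The opening of Section 7 names the periodic telephone form as the means of capturing AEs. Section 7.2 sets how often it is used: "Study staff will contact participants up to 3 times during the intervention". Section 6.1.3 requires at least one call in each of the two blocks of telephone sessions.

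The form itself is in Appendix A.1. One recall phrase, "In the past week", governs all its items. Items a to d cover serious events and do not ask about cause; the participant is asked, for example, whether they have "been hospitalized for any reason" or "become physically disabled in some way". The emotional-health item is also asked without regard to cause, and the participant's view of relatedness is noted only after a yes. The last item, on physical health, asks whether the participant has "experienced any new or worsening physical health problems that you think might be related to being part of this study".

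Under Sections 7.1 and 7.5, relatedness is determined by the investigators and the Study Physician.

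**The concern.** There are two separate mismatches.

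**Recall.** A participant hospitalized two weeks before a call can truthfully answer no to every item. No question on the form reaches back to the previous contact or to enrollment.

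**Attribution.** For general, non-serious physical complaints, the participant decides on relatedness before anyone on the study team hears of the event. Section 7 lists headaches, aches, nausea, sweating and rapid heart rate as possible effects of the intervention. A caregiver could easily put these down to something else. The possibly-related grade in Section 7.3 is meant for events with several plausible causes, and those are the ones a participant is likely to screen out.

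The reports to the Safety Monitoring Committee (Sections 7.4 and 7.6) and the stopping rule of three individuals with related serious events (Section 9.3) depend on what is captured. The 24-hour reporting clock in Sections 7.2 and 7.4 starts only when staff receive a participant's report. Safety summaries could therefore look cleaner than the protocol's own AE definition warrants.

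**Working it through.** The plan gives no figure for AE capture, so there is none to reproduce. The check is a coverage calculation followed by a comparison of texts.

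**Inputs**
- Recall per call: 1 week (Appendix A.1).
- Calls: at least 2 (one in each of two blocks, Section 6.1.3); at most 3 (Sections 7 and 7.2).
- Intervention: 8 weeks (Précis).
- Participation in Table 2: baseline between W-4 and W0, final visit by W15. Section 6.1.4 places the final assessment within 4 weeks of the last session, about W12 (8 + 4).

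**Formula.** Share of time asked about = (windows × 1 week) / weeks in the period. This is the best case: the windows do not overlap and all fall inside the period.

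**Intervention only**
- 2 / 8 = 25%
- 3 / 8 = 37.5%
- Not asked about by the form: 62.5% to 75% of the 8 weeks.

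**Whole period, calls only**
- W0 to W15: 2/15 = 13.3% to 3/15 = 20.0%
- W-4 to W15 (19 weeks): 2/19 = 10.5% to 3/19 = 15.8%

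**Whole period, assuming the final visit uses the same form and recall.** Table 2 marks an AE assessment at that visit but names neither instrument nor recall period. One window is added:
- W0 to W12: 3/12 = 25% to 4/12 = 33.3%
- W0 to W15: 3/15 = 20.0% to 4/15 = 26.7%
- W-4 to W15: 3/19 = 15.8% to 4/19 = 21.1%

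Under every choice of period, most of the time is outside the form's questions.

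**Attribution, item by item**
- Items a to d (hospitalization, life-threatening event, birth defect, disability): asked regardless of cause. Consistent with Section 7.3.
- Emotional health: asked regardless of cause, relatedness noted afterward. Consistent with Section 7.3.
- Physical health: asked only if the participant suspects a link. Not consistent with Section 7.3, and only conditionally consistent with Section 7.1, which says check-ins cover both psychological and physical health.

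**Other routes**
- Self-report in sessions and instructor prompts (Sections 7 and 7.2): depend on the participant raising a difficulty in class.
- Attendance tracking (Section 5.3, Adherence Assessment, and Section 6.1.3): records absence; no question about its cause is stated.
- Inquiry at withdrawal (Section 6.1.4): concerns AEs that may have led to stopping.
- Calls to people who withdraw but stay in follow-up (Section 8.1): use the same form, hence the same recall.
- Weekly check-ins (Section 7.5): follow AEs already known.
- Final-visit AE assessment (Table 2): no stated instrument or recall.

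None of these states a question covering the time since the last contact, or a general physical question free of attribution.

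**The case against.** The strongest reply is that the form is not the only channel. Ongoing collection can mean periodic questioning combined with continuous receipt of reports. Participants are encouraged to report symptoms, instructors alert staff, attendance is sent in weekly, and the care partner is in the same program. A hospitalization would often surface through one of these. Asking selectively about minor physical complaints can also be defended in a study that describes its risks as minimal, and Section 7 itself ties aches and headaches to the practices. AE rates are neither a primary nor a secondary outcome.

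Much of this stands, and it rules out two stronger readings.

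- A reader might infer that the attribution filter hides serious physical events. It does not: items a to d are asked whatever the cause, and the filtered item says only that a link might exist.
- A reader might turn the coverage figures into a share of events missed, or cube them (0.375³ = 5.3%) and conclude that three serious events would rarely all be seen, so that the stopping rule fails. The documents do not support this. Such figures assume events that are independent and evenly spread, with none reported by any other route. The rule in Section 9.3 also counts only events probably or definitely related to the study, which are among the likeliest to surface through an instructor or a withdrawal inquiry.

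What the reply does not remove is the contradiction in the text. The named capture tool, followed as written, does not ask for what Sections 7.3 and 7.6 say will be collected, and no other route is specified to fill the gap.

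**Conclusion.** Both mismatches hold. The recall limit affects every item: in the best case the form asks about 25% to 37.5% of the 8 intervention weeks, and about 10.5% to 33.3% of the longer periods, depending on where the period starts and ends and whether the final visit uses the form. These are shares of time asked about. The share of events missed cannot be derived from the documents. The attribution limit affects only the general, non-serious physical item.

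The coverage figures assume a one-week window per call, no overlap, and 2 to 3 calls. The conflict in wording needs none of these assumptions.

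**What to change.** In Appendix A.1:

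1. Replace the one-week recall with *since you enrolled* at the first call and *since we last spoke on [date]* thereafter. Counting from enrollment matters because consent can precede the first session (Section 6.1.2; baseline from W-4 in Table 2), and Section 7.6 starts the clock at study start.
2. For the emotional item, also record whether the problem was present in the past 7 days. A yes triggers the PROMIS Anxiety short form, which covers the past 7 days (Table 3), so the two must stay aligned.
3. Delete the closing condition on the physical item and record perceived relatedness as a follow-up, as the emotional item already does.
4. State in Section 6.1.4 and Table 2 that the same form and recall are used at the final visit.

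The cost is a few wording changes and an IRB modification, with no added calls. The downsides are small: more minor, unrelated complaints to log and grade, and somewhat longer recall. If data collection is already complete, safety reports should state the form's recall and attribution limits.
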